A randomized, multicenter, double-blind, placebo-controlled comparison of standard (neo)adjuvant therapy plus placebo versus standard (neo)adjuvant therapy plus atorvastatin in patients with early breast cancer.

Cholesterol-lowering drugs such as statins are currently used to lower cholesterol levels and prevent cardiovascular events. Statins have, however, received substantial scientific attention as cancer-inhibiting drugs. Previous findings were recently supported in a large-scaled study again demonstrating the beneficial effects of statins on breast cancer outcome this time nested within a large, international, randomized clinical trial of modern adjuvant cancer therapy. Given the compelling evidence supporting a protective effect of statins on breast cancer recurrence, calls for prospective clinical trials have been expressed. In this trial – the MASTER trial – we hypothesize that the addition of statin treatment to the current breast cancer treatment will improve the prognosis of women with early breast cancer. Thus, the primary objective of the MASTER trial is to determine the clinical efficacy of the statin – atorvastatin – as measured by invasive disease-free survival among patients with primary breast cancer.

The trial is nationwide throughout Denmark and a total of 3,360 women are to be included in the trial. Women eligible for the trial have been diagnosed with an estrogen receptor positive breast cancer and are candidates for systemic cancer therapy, either prior to or following breast surgery. Upon eligibility and signed informed consent, trial participants will be randomized in a 1:1 manner to either standard treatment and atorvastatin 80 mg/day or standard treatment and placebo. The randomization is blinded. The treatment with atorvastatin or placebo will continue for two years unless side effects are experienced and further treatment with atorvastatin or the placebo is deemed inadequate. The standard treatment will of course continue as planned. The trial participants will follow the standard clinical routines in terms of follow-up and in addition they are asked to fill in questionnaires, i.e. regarding potential side effects, up to ten years following inclusion. Potential breast cancer recurrences are identified through follow-up and a follow-up of at least $6^1/2$ years will be required for the trial the demonstrate the estimated clinical difference between the randomized groups of patients.

TRIAL SYNOPSIS

TITLE	A randomized, multicenter, double-blind, placebo-controlled comparison of standard (neo)adjuvant therapy plus placebo versus standard (neo)adjuvant therapy plus atorvastatin in patients with early breast cancer.				
SPONSOR	Aarhus University Hospital				
OBJECTIVES	PRIMARY OBJECTIVES				
	To compare invasive disease-free survival (IDFS) in patients randomized to standard (neo)adjuvant therapy plus placebo or standard (neo)adjuvant therapy plus atorvastatin (80 mg/day for two years).				
	SECONDARY OBJECTIVES				
	- To compare overall survival (OS), recurrence-free interval (RFI), distant recurrence-free interval (DRFI) including associations with first site of recurrence, cardiac death-free interval, and overall safety in the two treatment arms.				
	- To evaluate pathological response (only neoadjuvant treated patients) according to treatment arm				
	- To investigate patient reported outcome measurements.				
	- To address translational endpoints as specified in the translational protocol parts.				
TRIAL DESIGN	A prospective, two-armed, randomized (1:1), multicenter, national, double-blind, placebo-controlled study in early breast cancer patients.				
NUMBER OF PATIENTS	N=3,360 participants.				
TARGET POPULATION	Early cohort; randomization before start of (neo)adjuvant therapy.				
	Late cohort; randomization after start of adjuvant therapy, but within three years of initiation of the endocrine treatment.				
	Observational cohort; non-randomized cohort of patients already on cholesterol-lowering medication at the time of diagnosis.				
INCLUSION CRITERIA	Patients must meet ALL of the following criteria to be eligible for randomization:				
	 Women with estrogen receptor positive breast cancer who are candidates for (neo)adjuvant systemic therapy OR have received ≤3 years of adjuvant endocrine therapy. Age > 18 years. Performance status of ECOG ≤ 2. Prior to patient registration, written informed consent must be given according to ICH/GCP, and national/local regulations. 				
EXCLUSION CRITERIA	 Patients meeting ANY one of the following criteria are not eligible: History of any prior (ipsi- and/or contralateral) invasive breast carcinoma. Ongoing (prevalent) cholesterol-lowering therapy (statins, fibrates, ezetimibe, PCSK9 inhibitors). If so, the patient can be enrolled in the observational arm given fulfillment of other inand exclusion criteria. 				

- Reduced performance status (ECOG>2) will require permanent discontinuation of STUDY MEDICATION.

DURATION OF THERAPY

All patients will receive STUDY MEDICATION (atorvastatin or placebo) for two years.

STUDY MEDICATION will be discontinued if:

- 1. There are any SAFETY concerns.
- 2. Cholesterol-lowering therapy becomes clinically indicated.
- 3. Discontinuation is requested by the participant and/or her treating physician.
- 4. In case of an incident breast cancer event (any invasive breast cancer, including local/regional, contralateral or distant recurrence).

Atorvastatin is a well-documented drug prescribed for continuous use over several years and the appearance of other illnesses would not indicate discontinuation of atorvastatin.

CONCOMITANT THERAPY

During STUDY MEDICATION concomitant drugs are permitted. Caution should be taken in case of:

- Digoxin treated patients should be monitored as coadministration of atorvastatin and digoxin has been shown to increase steady-state plasma digoxin concentrations by approximately 20%. Among digoxin-treated patients, plasma digoxin will be measured at baseline, after 1 week and after 1 month on STUDY MEDICATION and an increase of ≥ 20% at consequently will lead to a reduction in dosage of digoxin.
- 2. Daily intake of grapefruit juice should be avoided during atorvastatin therapy due to the grape fruit induced inhibition of CYP450 system by which atorvastatin is metabolized.
- 3. CYP3A4 inhibitors such as macrolide antibiotics (erythromycin), immunosuppressants (cyclosporine), azole antifungal agents (*i.e.*, itraconazole, ketoconazole), and some antidepressants (*i.e.*, nefazodone) should if possible be avoided during atorvastatin therapy as they may have a potential of increasing plasma concentrations of atorvastatin.

PROCEDURES (Summary)

During STUDY MEDICATION, patients will be assessed for safety and efficacy (see Schedule of Assessments tables).

Patients will receive STUDY MEDICATION for a total of two years (104 weeks).

ASSESSMENTS

EFFICACY

IDFS, defined as the time from randomization until the date of the first occurrence of one of the following events:

- Ipsilateral invasive breast tumor recurrence: invasive breast cancer involving the same breast parenchyma as the original primary.
- Regional invasive breast cancer recurrence: Invasive breast cancer in the axilla, regional lymph nodes, chest wall, and skin of the ipsilateral breast.
- Distant recurrence: Metastatic disease-breast cancer that has either been biopsy confirmed or clinically diagnosed as recurrent invasive breast cancer.
- Death attributable to any cause, including breast cancer, nonbreast cancer, or unknown cause.
- Contralateral invasive breast cancer.
 - Second primary non-breast invasive cancer.

SAFETY

Any adverse events (AE's) will be recorded according to clinical routine during active treatment and their frequencies reported. Toxic effects will be categorized using a modified version of the NCI Common Terminology Criteria for Adverse Events, Version 5.0.

STATISTICAL ANALYSES

PRIMARY EFFICACY ENDPOINT

The primary efficacy variable is IDFS and is defined as the time between randomization and date of first occurrence of an IDFS event (as defined above in efficacy assessments).

The intention-to-treat (ITT) population will be used in the primary analysis.

The stratified log-rank test will be used to compare IDFS between the two treatment arms.

SECONDARY EFFICACY ENDPOINTS

Pathological response (neo-adjuvant patients only)

Recurrence-Free Interval

Distant Recurrence-Free Interval including associations with first site of recurrence

Overall Survival

Death attributable to any cause, including non-breast cancer or unknown cause, is considered a competing event.

Cardiac death-free interval. Cardiac death is defined as:

- Definitive cardiac death due to heart failure, myocardial infarction or documented primary arrhythmia.
- Probable cardiac death defined as sudden, unexpected death within 24 hours of a definite or probable cardiac event (e.g., syncope, cardiac arrest, chest pain, infarction, arrhythmia) without documented etiology.

Overall safety

Patient Reported Outcome

Translational biomarker endpoints (stated below)

SAFETY ANALYSES

Randomized patients who receive any amount of STUDY MEDICATION will be included in the safety analyses. Safety will be summarized by the amount of treatment actually received.

SAMPLE SIZE

The sample size calculations are based on estimates of 10-year IDFS with an annual hazard rate of 0.0223. A sufficient number of patients is sought to provide 80% power using a two-sided 0.05-level test to detect a 25% reduction in the risk of an IDFS event (hazard ratio=0.75). A total of 379 events are required. With an estimated 5% drop-out at 5 years (annual rate 0.0103), this is estimated to be achieved by a total recruitment of 3,360 participants and a $6\frac{1}{2}$ years follow-up. The sample size estimate is

based on inclusion for 3 years, a median follow-up of 6½ year, that is 5 years of additional follow-up after the 3 years of inclusion.

TRANSLATIONAL STUDIES

BLOOD SAMPLES

Trial participants are asked for blood samples collected at baseline, after one and two years of study treatment, respectively, and in case of early withdrawal or recurrence while on study treatment. Particularly for neoadjuvant patients, an additional blood sample will be drawn at the time of stopping chemotherapy/prior to surgery. Samples are stored in a research biobank established for this study. Circulating biomarkers will be analyzed for their predictive and prognostic value. Samples are stored as plasma, serum, buffy coat, and whole blood at minus 80-degree Celsius at the Departments of Biochemistry of participating hospitals and final storage at the Danish Cancer Biobank.

TUMOR TISSUE SAMPLES

Archived tumor tissue from the primary breast tumor will be sampled in tissue micro arrays, which are then stores in a research biobank. Triplicate cores of 1 mm in diameter will be sampled from the donating tumor block and mounted in a recipient paraffin block, which will be able to host tumor cores from 50-60 tumors per paraffin block. Primary tumor tissue will be analyzed for the expression of cholesterol associated biomarkers, including i.e. HMGCR, LDL-receptor, and CYP27A1. One of the tumor tissue cores will be sampled for RNA-extraction and further gene expression analyses using the Illumina Platform. Tumor tissue analyses will allow for identification of prognostic and treatment predictive factors and pave the way for more personalized (neo)adjuvant treatment.

TABLE OF CONTENTS

1		BAC	CKGR	OUND AND INTRODUCTION	11
	1.1	1	Вас	kground disease information	11
	1.2	2	Bac	kground therapeutic information	14
2		OBJ	ECT1	IVES OF THE TRIAL	15
	2.1	1	Prin	nary objective	15
	2.2	2	Sec	ondary objectives	15
	2.3	3	End	points	15
3		PAT	IENT	SELECTION CRITERIA	16

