7 CRITERIA OF EVALUATION

Evaluable for toxicity

All patients will be evaluable for toxicity from the time of their initiated treatment with atorvastatin (T1) and until discontinued treatment (T5).

Evaluable for response

All eligible patients will be included in the response rate calculation. The subset that will be assigned a response category (see definitions below) are all patients who have received two years of minimum 80% of full dosage atorvastatin.

Response and Evaluation Endpoints

- Response according to primary endpoint:
- Atorvastatin response according to invasive disease-free-survival (IDFS) will be assigned significant in case of a significant improved IDFS. Recurrences cover all invasive recurrences.
- Response according to secondary endpoints:
- Clinical survival endpoints will be evaluated by follow-up within the trial and annual linkage to the national death registry.

All statistical analyses will be performed for the entire study population as well as in exploratory analyses separately as stated in section 2.3 order to detect a potential differentiated effect of atorvastatin depending on the clinical setting.

- Translational endpoints are described in section 10.
- Patients reported outcome are evaluated and related to differences between treatment arms in incidence of recorded symptoms.

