14.2 Reporting procedure

Any SAE occurring from start of STUDY MEDICATION until 30 days after termination of STUDY MEDICATION should be reported to the sponsor center, Department of Oncology, Aarhus University Hospital, within 24 hours from the time the investigator became aware of the event (expedited reporting). A template for reporting serious adverse events (SAE) is provided all trial sites and upon an SAE, the filled SAE template is to be email to the sponsor site ([contact]). The SAE is implemented into the database and reported according to national regulations. Related SAEs MUST be recorded and reported, regardless of the time elapsed between the last study drug administration, even if the trial is completed. Non-related SAEs occurring during the trial until 28 days after the last dose of STUDY MEDICATION must be recorded and reported. Related SAEs are to be recorded and reported up to 24 months after completion of STUDY MEDICATION. Sponsor will report serious adverse and/or unexpected serious and suspected adverse reactions (SUSARs) as needed to investigators, the Medical Products Agency and the ethics committee in accordance with the relevant legal requirements and ICH's quidelines for Good Clinical Practice (GCP). Hereof, SUSARs, which are deadly or life threatening, are to be registered and reported to the Medical Product Agency as quickly as possible and at the latest 7 days after sponsor has been aware of such a presumed adverse event. All other SUSARs are to be reported to the Medical Product Agency later than 15 days after the sponsor has been notified.

Unblinding: In case an emergency in which unblinding of STUDY MEDICATION is deemed necessary, the procedure is as follows:

1. The patient, relatives or health personnel will find and can call the phone number stated at the trial specific card, which the participants receive upon inclusion, indicating the phone number to the Department of Oncology at their specific site, i.e. for Aarhus University Hospital:

Patienten deltager i et videnskabeligt forsøg:

KFE-XXXX - KALDENAVN Forsøgets titel: xxxxxxxxx

Forsøgsansvarlig læge: xxxlæge xxxxx xxxxx

Inden for 24 timer skal Klinisk Forsknings Enhed have besked om indlæggelsen på e-mail [contact].

Vagthavende på Kræftafdelingen: Tlf. [name]

2. Each site has staff at the hospital, who can unblind patients immediately, and each site must make a local, written procedure for unblinding.

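### The safety summary is grouped by amount of treatment received, which toxicity itself determines, instead of by arm; separately, the adverse-event and SAE collection periods contradict each other

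*Protocol*

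**What the plan says.** Synopsis, Safety analyses: the safety set is every randomized patient who took some study medication, and "Safety will be summarized by the amount of treatment actually received". No arm is named there. Synopsis, Secondary objectives: overall safety is to be compared between the two arms.

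Synopsis (Dose adjustments and Duration of therapy) and Section 5.1.4: raised transaminases, intolerable related events, myopathy and safety concerns stop study medication. After some of these it may be restarted.

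On the collection period:

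- Synopsis, Safety assessments, and Section 8.2, Safety Monitoring: adverse events are followed during active treatment.
- Section 7: "All patients will be evaluable for toxicity from the time of their initiated treatment with atorvastatin (T1) and until discontinued treatment (T5".
- Section 5.1.4: after early stopping, everything except the study medication goes on.
- Section 6.5, Summary table 1: the adverse-event form is scheduled from T1 to T5, the two-year visit.
- Section 14.2, all SAEs: "Any SAE occurring from start of STUDY MEDICATION until 30 days after termination of STUDY MEDICATION should be reported".
- Section 14.2, non-related SAEs: "Non-related SAEs occurring during the trial until 28 days after the last dose of STUDY MEDICATION must be recorded".
- Section 14.2, related SAEs: "Related SAEs MUST be recorded and reported, regardless of the time elapsed" and, later in the same paragraph, "Related SAEs are to be recorded and reported up to 24 months after completion of STUDY MEDICATION".
- Section 14.2, SUSARs that are not fatal or life-threatening: they "are to be reported to the Medical Product Agency later than 15 days after the sponsor has been notified".

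**The concern.** A patient who stops because of an adverse event has, for that reason, received less drug. A table grouped by amount therefore places toxic cases in the low-exposure rows whether or not atorvastatin causes them. Even if each row is split by arm, the patients compared within it are no longer comparable by randomization, because they were selected on something that happened after it. At stake is whether the published safety table answers the stated objective of atorvastatin against placebo.

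The collection period is a different problem. A site cannot follow two end points for the same SAE. If adverse-event collection stops when the patient stops the drug, its length can differ between arms whenever discontinuation does.

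**Working it through.** The plan gives no safety rates, so there is no figure of its own to reproduce. The illustration below rests on assumed rates.

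**A. Grouping by amount**

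From the protocol: two years of treatment, 1:1 allocation, adverse events as a cause of stopping. The 80% cut is borrowed from Section 7, which uses it for response; the safety rule gives none.

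Assumed: adverse-event hazard h per year; a fraction q of adverse events stops the drug for good; other discontinuation at hazard o per year. Events count to 30 days after stopping, d = 30/365.25 = 0.082 years. Low amount means stopping before 1.6 years (80% of 2).

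With K = 1 − exp(−1.6(h+o)):

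- Share with low amount: L = 1 − exp(−1.6o)·[1 − q(1 − exp(−1.6h))]
- Low amount and an event: E = q·hK/(h+o) + (1−q)·[1 − exp(−1.6o) − exp(−hd)·oK/(h+o)] + q(1 − exp(−hd))·oK/(h+o)
- Any counted event: P = 1 − exp(−hd)·[(o/(h+o))(1 − exp(−2(h+o))) + exp(−2(h+o))]
- Risk at low amount is E/L; at 80% or more it is (P − E)/(1 − L).

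*One arm, no drug effect* (h = 0.10, o = 0.10, q = 0.7): L = 0.236, E = 0.100, P = 0.172. Risk is 0.100/0.236 = 0.42 at low amount and (0.172 − 0.100)/0.764 = 0.09 at 80% or more. With q = 0.3 the pair is 0.27 and 0.15.

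*Two arms, no drug effect, more other discontinuation on atorvastatin* (o = 0.20 against 0.10, q = 0.7): on atorvastatin L = 0.349 and E = 0.097, so risk at low amount is 0.278. Against 0.425 on placebo the ratio is 0.65; with q = 0.3 it is 0.66.

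| h, atorvastatin vs placebo | o, atorvastatin vs placebo | Full two years | On treatment + 30 days | Under 80%, q = 0.3 / 0.7 |
|---|---|---|---|---|
| 0.10 vs 0.10 | 0.10 vs 0.10 | 1.00 | 1.00 | 1.00 / 1.00 |
| 0.10 vs 0.10 | 0.20 vs 0.10 | 1.00 | 0.92 | 0.66 / 0.65 |
| 0.15 vs 0.10 | 0.10 vs 0.10 | 1.43 | 1.43 | 1.33 / 1.24 |
| 0.15 vs 0.10 | 0.20 vs 0.10 | 1.43 | 1.31 | 0.91 / 0.86 |

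The last four columns' entries are risk ratios, atorvastatin to placebo, except that the second column gives the assumed o. The full-period 1.43 is (1 − exp(−0.30))/(1 − exp(−0.20)) = 0.259/0.181. In the last row the low-amount group reverses the direction of a real excess.

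**B. Collection periods side by side**

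- Non-related SAEs, 30 against 28 days: over two years plus tail, (730.5 + 30)/(730.5 + 28) = 760.5/758.5 = 1.003, so about 0.3%. This is a real conflict but numerically trivial.
- Related SAEs, no limit against 24 months: an event judged related 30 months after the last dose is reportable under one sentence and not under the other.
- Other adverse events: Section 7 treats discontinuation and T5 as the same date. They coincide only for completers. For a patient who stops at month 6 they are 24 − 6 = 18 months apart. Active-treatment recording ends at month 6, while Sections 5.1.4 and 6.5 carry the form to month 24. The on-treatment column above shows what the shorter reading can do when discontinuation differs: 1.00 becomes 0.92, and 1.43 becomes 1.31.
- Other SUSARs: the sentence before sets an upper limit of 7 days for fatal or life-threatening cases. Read literally, the 15-day sentence sets a minimum delay.

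**The case against.** The synopsis sentence may simply be loose wording for treatment actually received. The objective names the arms, and Section 7 compares arms for patient-reported symptoms: "Patients reported outcome are evaluated and related to differences between treatment arms in incidence of recorded symptoms". Detailed tables belong in a statistical analysis plan, which is not at hand. This stands as far as intent goes: no passage pools the arms or drops the arm comparison, so a reader who infers that the trial cannot say whether atorvastatin is more toxic than placebo goes too far. It does not rescue the sentence, which is a stated rule and not a gap, says amount, and names no arm.

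The rates are assumed, and Section 5.1.4 allows restarting, so an event-related stop need not mean a low total amount. That stands and weakens the size of the effect, not its direction.

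Section 7 defines who is evaluable and Section 14.2 governs expedited reporting, so their periods may legitimately differ. That also stands. The contradictions inside Section 14.2, and between recording on treatment only and continued procedures, remain.

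A reader might also infer that patient-reported symptoms will be analysed without their baseline. Section 7 does not say so, the baseline is collected at T1, and adjustment can be left to the analysis plan.

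**Conclusion.** The safety grouping rule is badly fixed and should be corrected. Taken literally, it sorts patients by a post-randomization variable that toxicity drives, and it does not match the stated objective. The distortion between arms depends on unequal discontinuation: under the assumed rates it runs from none when discontinuation and event rates are equal, to a ratio of 0.65 in place of 1.00, or a reversal from 1.43 to about 0.9. The false gradient by exposure within an arm (0.42 against 0.09, or 0.27 against 0.15) needs only that some adverse events stop treatment.

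The collection periods are a separate defect of definition. It is tempting to say that the conflicting SAE periods make the comparison non-randomized. They do not: the same text applies to both blinded arms. They leave the period, and hence the count of late events, undefined. The 28/30-day conflict is trivial in size, the related-SAE conflict is material for late events, and the 15-day wording is probably a slip in operative reporting text.

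**What to change.** 1. Synopsis, Safety analyses: replace the sentence with a statement that safety is summarized by treatment arm (atorvastatin or placebo) in randomized patients who took any study medication, and that the amount taken is described separately by arm.

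2. Reconcile the Synopsis (Safety assessments) and Sections 5.1.4, 6.5, 7, 8.2 and 14.2, so that one stated adverse-event collection period applies to both arms whether or not study medication was stopped early, with one rule each for non-related and related SAEs. Which period to use is for the sponsor to decide. In Section 7, refer to study medication and not to atorvastatin alone.

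3. Section 14.2: reword the 15-day sentence as a deadline, as the 7-day sentence already is.

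All three are wording changes. The grouping change needs no new data, and the adverse-event form is already scheduled through T5. Sites need to be told which periods apply.

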5.1.4 Early stopping rules

- Raising levels of hepatic transaminases to three times the upper limit of normal will require discontinuation of STUDY MEDICATION therapy until normalized hepatic function has returned. Upon normalization, the STUDY MEDICATION can be re-induced.
- Intolerable adverse events deemed related to STUDY MEDICATION (answered "Probable" or "Certain" in CRF), will require discontinuation of STUDY MEDICATION. Upon normalization, the STUDY MEDICATION can be re-induced.
- Myopathy (muscle aching or muscle weakness in conjunction with increase in creatinine phosphokinase values greater than five times the upper limit of normal) will require permanent discontinuation of STUDY MEDICATION.
- Reduced performance status (ECOG>2) will require permanent discontinuation of STUDY MEDICATION.

In case of early stopping of STUDY MEDICATION, all other procedures will continue apart from STUDY MEDICATION. It should be registered in the CRF folder "Master End of Trial" if the patient stops medication (End of treatment) and if the patients for any reasons stops participating in this study (End of trial).

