The study was initiated in January 2021. The estimated nation-wide accrual rate is 90 patients per month. Thus, patient accrual is expectedly completed within 4 years. Treatment duration time adds two years and the initial observational period adds another 5 years. In total, the time frame from study start to 5-year recurrence data is estimated to 10 years.

Given the bulk of patients with ongoing endocrine therapy who are eligible for the late entry stratum of the trial, this will be very pronounced within the beginning of the trial accrual.

All of the patients registered in the study will be accounted for besides patients already on a cholesterol-lowering drug who are enrolled in the observational cohort. The number of patients who were not evaluable, or who died or withdrew before treatment with STUDY MEDICATION began, will be specified. The distribution of follow-up time will be described, and the number of patients lost to follow-up will be provided.

Safety Monitoring

Adverse events will be recorded in the MASTER trial CRF in the DBCG database and monitored on an ongoing basis during active treatment and their frequencies reported to the sponsor equal to the coordinating national trial site, Department of Oncology, Aarhus University Hospital. Toxic effects will be categorized using a modified version of the NCI Common Terminology Criteria for Adverse Events, Version 5.0.

For reporting of adverse events, please see protocol chapter 14.

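### The synopsis groups the safety summary by amount of drug received and does not name the arm, which does not match the stated objective of comparing safety between arms

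*Protocol*

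**What the plan says.** The safety rule is in the synopsis, under Statistical analyses, Safety analyses. It has two parts.

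- Population: "Randomized patients who receive any amount of STUDY MEDICATION will be included in the safety analyses".
- Summary: "Safety will be summarized by the amount of treatment actually received".

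The safety objective is in the synopsis under Secondary objectives. The trial is to compare, among other outcomes, "cardiac death-free interval, and overall safety in the two treatment arms". Section 2.3 lists overall safety as secondary endpoint E.

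The other statements on adverse events name no grouping variable. The synopsis assessments say "Any adverse events (AE's) will be recorded according to clinical routine during active treatment and their frequencies reported". Section 8.2 (Safety Monitoring) has events "monitored on an ongoing basis during active treatment and their frequencies reported to the sponsor", with grading by a modified CTCAE. Arm is named for one related outcome, in section 7: "Patients reported outcome are evaluated and related to differences between treatment arms in incidence of recorded symptoms".

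Toxicity affects how much drug a woman takes. Section 5.1.4 requires discontinuation for raised transaminases, for "Intolerable adverse events deemed related to STUDY MEDICATION", and for myopathy. The first two allow treatment to restart after normalization; myopathy does not. The synopsis (Duration of therapy) adds any safety concern as a reason to discontinue.

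**The concern.** The any-dose population is conventional and raises no problem. The difficulty is the grouping variable.

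First, amount does not identify the treatment. Study medication means atorvastatin or placebo, so a woman who took all her placebo and a woman who took all her atorvastatin have received the same amount. A table grouped by amount alone does not separate them and so does not answer the stated objective.

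Second, amount is not fixed at randomization. A woman who stops because of an adverse event falls into a lower-amount group because of that event. A woman who stays on treatment longer has more time to have an event recorded. Both mechanisms link frequency to amount without any drug effect, and they pull in opposite directions.

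At stake is a named secondary endpoint. A reader could take a gradient by amount as evidence about dose and toxicity when it reflects only stopping behaviour.

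**Working it through.** **Setting the passages side by side.** The objective requires a contrast between arms. The only grouping rule names amount. The adverse-event statements in the synopsis and section 8.2 name neither. Section 7 names arm, but only for patient-reported symptoms. The mismatch is therefore in the text and needs no arithmetic.

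**Can a gradient by amount arise with no drug effect?** The protocol gives no adverse-event incidence, no share of women stopping for events, no lengths of interruption and no exposure categories for safety. The only figure taken from it is the two-year (24-month, 104-week) treatment period. The rest is assumed:

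- 10% risk of a first event over 24 months in both arms, at constant hazard
- 10% stopping for unrelated reasons, at constant hazard
- a share *s* of affected women stopping permanently at the event
- events counted only while on treatment
- amount = months on drug / 24

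With *q* = 0.9, the probability of being event-free at fraction *x* of the period is *q*^*x*. The same expression holds for not having stopped for another reason.

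*Amount below 50% (x = 0.5).*

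- Women who would stop at an event: fraction in the group = 1 − *q*^(2*x*) = 0.100; with an event = half of that = 0.050.
- Women who would not: fraction in the group = 1 − *q*^*x* = 0.0513; with an event = 0.0513 − 0.050 = 0.0013.
- Event proportion = [0.050*s* + 0.0013(1 − *s*)] / [0.100*s* + 0.0513(1 − *s*)].

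*Amount 80% or more (x = 0.8).*

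- Women who would stop at an event: fraction in the group = *q*^1.6 = 0.8449; with an event = ½(*q*^1.6 − *q*^2) = 0.0174.
- Women who would not: fraction in the group = *q*^0.8 = 0.9192; with an event = 0.9 × 0.1 + (0.9192 − 0.9 − 0.0174) = 0.0917.
- Event proportion = [0.0174*s* + 0.0917(1 − *s*)] / [0.8449*s* + 0.9192(1 − *s*)].

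The table shows these formulas beside a simulation under the same assumptions, both arms pooled (simulated values in brackets).

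| Share stopping at the event, *s* | Below 50% of planned drug | 80% or more | Lowest ÷ highest |
|---|---|---|---|
| 0 | 2.6% (2.6%) | 10.0% (10.0%) | 0.26 |
| 25% | 21.2% (20.9%) | 8.1% (8.1%) | 2.6 |
| 50% | 33.9% (34.1%) | 6.2% (6.2%) | 5.5 |
| 90% | 47.4% (47.4%) | 2.9% (2.9%) | 16 |

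The direction depends on *s*. At *s* = 0.08 the two proportions are nearly equal: 0.00521/0.05521 = 9.4% and 0.08579/0.91322 = 9.4%. In the simulation the placebo arm shows the same gradient as the atorvastatin arm, as it must with no drug effect.

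A second simulation used cuts at 25% and 80%, 15% stopping for other reasons, incidence of 5 to 20% and stopping shares of 30 to 70%. Lowest against highest group: 9.3% against 3.9% (ratio 2.4), 24.8% against 6.2% (4.0), 49.3% against 9.6% (5.1) and 18.1% against 2.2% (8.2).

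**The same data by arm.** With no drug effect, the first simulation gives 9.4 to 9.6% in each arm at every stopping share, so no false difference. With an assumed true risk of 10% against 5%, it gives 9.4 to 9.6% against 4.7 to 4.8%, which recovers the contrast. Pooled by amount at *s* = 50%, that second case gives 27.9% below half of planned drug and 4.6% at 80% or more, with the arm difference not visible.

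**The case against.** The strongest reply is that the sentence is loose rather than wrong. It is silent on arm and does not exclude tables by amount within arm. The objective commits to comparing arms, and section 7 does so for patient-reported symptoms. The authors may have meant the usual as-treated convention, with the words about amount slipping in. Table layout is normally left to the statistical analysis plan, which is not at hand.

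Much of this stands. A reader might infer that the protocol abandons the randomized safety comparison. The documents do not support that: the arm comparison remains a stated objective.

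A reader might also infer that the table would certainly show most toxicity in the women who took least drug. That is not supported either. Section 5.1.4 allows treatment to restart after raised transaminases and intolerable events. Of 104 weeks, 20% is 20.8 weeks, so an interruption of about 20 weeks still leaves a woman at 80% of planned drug. The simulations treat every event-driven stop as permanent, and with few such stops the gradient reverses. If placebo is shown beside atorvastatin, the same gradient in placebo would also warn the reader that it is an artefact.

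Two things remain. The protocol does fix a grouping variable, so this is not detail left open for a later plan, and the variable it fixes does not serve its objective. Splitting by amount within arm does not remove the gradient; it only makes it easier to recognise.

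**Conclusion.** The point holds as a mismatch between the safety-analysis sentence and the safety objective. The sentence names amount of drug as the only grouping variable for clinician-reported adverse events. Amount is determined partly by toxicity, so frequencies by amount can mislead in either direction without any drug effect.

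The size is unknown. The ratios of about 2 to 8 and 2.6 to 16 rest wholly on assumed incidence, stopping shares, cut-points and permanent stopping, and the reversed case (ratio 0.26) is equally a product of assumption. They show that the artefact can be large, not how large it would be in this trial.

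Severity is minor to moderate. The sentence appears once, in the synopsis, and concerns a secondary endpoint. Randomization, data collection and the primary analysis of invasive disease-free survival are unaffected, and by-arm tables can be produced from the same data.

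**What to change.** Replace the summary sentence in the synopsis with: *Safety will be summarized by treatment arm (atorvastatin or placebo, as actually received) in all randomized patients who received any STUDY MEDICATION, regardless of the amount taken.*

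Report exposure (duration and percentage of planned tablets) by arm in a separate descriptive table. If a breakdown of adverse events by amount is wanted, show it only within arm and label it descriptive. The statistical analysis plan should use the same wording.

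The cost is one sentence. No new data are needed and no patient's care changes. It is best done before any unblinded safety table is produced.
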